7.4 Blinding

Patient and investigator will not be blinded to the study treatment allocation due to the change in stool colour with oral iron intake. It is not possible to simulate this change with a placebo “dummy” drug for the control group.

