9.1.5 Expected Serious Adverse Events/Reactions

Serious adverse events that could be expected during the course of the study according to the SmPC include vomiting, haematemesis, gastrointestinal perforation, abdominal pain and dysphagia which could be related to the progression of the disease. Adverse events may also be anticipated in relation to any postoperative chemotherapy used. These would include anaemia, neutropenia (and consequences of sepsis), thrombocytopenia (and consequences of

coagulopathy), rashes, photosensitivity, taste/hearing disturbance, hair loss, discoloured urine, diarrhoea, oral ulceration and renal failure. These adverse events will be recorded in the CRF as significant clinical events.

Events which are not deemed secondary to the underlying cancer will be reported to the sponsor as a Serious Adverse Event within 24 hours of the Investigator becoming aware of the event.

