9.2 Recording and reporting of SAEs, SARs AND SUSARs

All AEs occurring during the study observed by the investigator or reported by the participant, whether or not attributed to study medication, will be recorded on the CRF. These adverse events will be recorded in the CRF. All SAEs assigned by the PI or delegate (or following central review) as both suspected to be related to IMP-treatment and unexpected will be classified as SUSARs and will be subject to expedited reporting to the Medicines and Healthcare Products Regulatory Agency (MHRA). The sponsor will inform the MHRA, the REC and Marketing Authorisation Holder (if not the sponsor) of SUSARs within the required expedited reporting timescales. All related AEs that result in a participant’s withdrawal from the study or are present at the end of the study, will be followed up until a satisfactory resolution occurs.

It will be left to the investigator’s clinical judgment whether or not an AE is of sufficient severity

to require the participant's removal from treatment. A participant may also voluntarily withdraw from treatment due to what he or she perceives as an intolerable AE. If either of these occurs, the participant will undergo an end of study assessment and be given appropriate care under medical supervision until symptoms cease or the condition becomes stable.

The severity of events will be assessed according to the Common Terminology Criteria for Adverse Events (CTCEA V 5.0) the following scale:

- Grade 1 Mild; asymptomatic or mild symptoms; clinical or diagnostic observations only; intervention not indicated.
- Grade 2 Moderate; minimal, local or non-invasive intervention indicated; limiting age appropriate instrumental ADL.
- Grade 3 Severe or medically significant but not immediately life-threatening; hospitalization or prolongation of hospitalization indicated; disabling; limiting self-care ADL.
- Grade 4 Life-threatening consequences; urgent intervention indicated.
- Grade 5 Death related to AE

The relationship of AEs to the study medication will be assessed by a medically qualified investigator. Any pregnancy occurring during the clinical study and the outcome of the pregnancy, will be recorded and followed up for congenital abnormality or birth defect.

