9.3 Responsibilities

Principal Investigator (PI):

Checking for AEs and ARs when participants attend for treatment / follow-up.

1. Using medical judgement in assigning seriousness, causality and whether the event/reaction was anticipated using the Reference Safety Information approved for the trial.
2. Ensuring that all SAEs are recorded and reported to the sponsor within 24 hours of becoming aware of the event and provide further follow-up information

as soon as available. Ensuring that SAEs are chased with the sponsor if a record of receipt is not received within 2 working days of initial reporting.

3. Ensuring that AEs and ARs are recorded and reported to the sponsor in line with the requirements of the protocol.

Chief Investigator (CI) / delegate or independent clinical reviewer:

1. Clinical oversight of the safety of patients participating in the trial, including an ongoing review of the risk / benefit.
2. Using medical judgement in assigning the SAEs seriousness, causality and whether the event was anticipated (in line with the Reference Safety Information) where it has not been possible to obtain local medical assessment.
3. Immediate review of all SUSARs.
4. Review of specific SAEs and SARs in accordance with the trial risk assessment and protocol as detailed in the Trial Monitoring Plan.
5. Assigning Medical Dictionary for Regulatory Activities (MedDRA) or Body System coding to all SAEs and SARs.
6. Preparing the clinical sections and final sign off of the Development Safety Update Report (DSUR).

Sponsor: (NB where relevant these can be delegated to CI)

1. Central data collection and verification of AEs, ARs, SAEs, SARs and SUSARs according to the trial protocol onto a database.

2. Reporting safety information to the CI, delegate or independent clinical reviewer for the ongoing assessment of the risk / benefit according to the Trial Monitoring Plan.
3. Reporting safety information to the independent oversight committees identified for the trial (Data Monitoring Committee (DMC) and / or Trial Steering Committee (TSC)) according to the Trial Monitoring Plan.
4. Expedited reporting of SUSARs to the Competent Authority (MHRA in UK) and REC within required timelines.
5. Notifying Investigators of SUSARs that occur within the trial.
6. Checking for (annually) and notifying PIs of updates to the Reference Safety Information for the trial.

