9.4 Notification of Deaths

All deaths will be reported to the sponsor irrespective of whether the death is related to disease progression, the IMP, or an unrelated event. This report will be issued within 24 hours of the study team being notified of the death.

Reporting urgent safety measures

If any urgent safety measures are taken the CI/Sponsor shall immediately and in any event no later than 3 days from the date the measures are taken, give written notice to the MHRA and the relevant REC of the measures taken and the circumstances giving rise to those measures.

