10 STATISTICS AND DATA ANALYSIS

10.1 Sample size calculation

No sample size calculation will be performed for this feasibility study. We will recruit a total of 40 patients to this trial (20 per arm), based on literature and guidance that 30 or more patients would be sufficient to estimate a parameter (Lancaster, Dodd et al. 2004)

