10.4 Interim analysis and criteria for the premature termination of the trial

The trial will be terminated if there is an unacceptable number of SUSARs or SARs. Any interim data analysis will be performed at the request of the DMC.

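### Sections 9.1.5, 9.3 and 9.4 give different rules for sending serious events to the sponsor, so SAE notifications and SAE totals by arm depend on which is followed and, under 9.1.5, on an unblinded attribution to cancer

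*Combined protocol and SAP*

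**What the plan says.** Section 9.1.4 defines a serious event by its outcome (death, threat to life, hospital admission and so on), not by its cause.

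Section 9.1.5 then names two groups of expected events. The first, attributed to the product information and said to be possibly linked to disease progression, is vomiting, haematemesis, gastrointestinal perforation, abdominal pain and dysphagia. The second is toxicity anticipated from postoperative chemotherapy. It includes sepsis following neutropenia, and renal failure. Of these events the section says: "These adverse events will be recorded in the CRF as significant clinical events". The next sentence reads: "Events which are not deemed secondary to the underlying cancer will be reported to the sponsor as a Serious Adverse Event within 24 hours".

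Section 9.3 gives the principal investigator a duty with no exemption by cause: "Ensuring that all SAEs are recorded and reported to the sponsor within 24 hours of becoming aware of the event". Section 9.4 adds: "All deaths will be reported to the sponsor irrespective of whether the death is related to disease progression".

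Three other provisions matter here. Under 9.2, all adverse events, "whether or not attributed to study medication, will be recorded on the CRF". Section 7.4 states: "Patient and investigator will not be blinded to the study treatment allocation". Section 10.4 says: "The trial will be terminated if there is an unacceptable number of SUSARs or SARs".

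**The concern.** A serious event that the investigator judges secondary to the cancer has two possible routes. Under 9.3 it reaches the sponsor within 24 hours. Under the natural reading of 9.1.5 it stays in the CRF under a different label. Nothing says which section prevails.

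What is at stake is the second look at causality. Section 9.1.2 counts an event as a reaction if either the reporting clinician or the sponsor suspects a link, and 9.2 allows SUSAR classification after central review. Neither can happen promptly if the investigator's own attribution to cancer stops the SAE report. The data monitoring committee is asked in 9.3 to find patterns not visible case by case, and a case-by-case filter upstream works against that.

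The filter is also applied by someone who knows the allocation, and no independent adjudication of this attribution is described. Any comparison of SAE counts between arms inherits that judgement if the counts are built from notifications.

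**Working it through.** The plan gives no SAE rate and no figure on this point, so there is nothing to reproduce. The check is a comparison of the rules, followed by an illustration of scale.

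**1. Route of a serious event under each section**

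| Serious event judged to be | 9.1.5 | 9.3 | 9.4 |
|---|---|---|---|
| Secondary to the cancer, not fatal | CRF only (implied) | Sponsor, 24 hours | Not applicable |
| Secondary to the cancer, fatal | CRF only (implied) | Sponsor, 24 hours | Sponsor, 24 hours |
| Listed chemotherapy toxicity | Unclear: the list puts it in the CRF, but it is arguably not secondary to the cancer, so the next sentence makes it reportable | Sponsor, 24 hours | Sponsor, 24 hours, if fatal |
| Neither secondary to the cancer nor listed | Sponsor, 24 hours | Sponsor, 24 hours | Sponsor, 24 hours, if fatal |

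The sections plainly disagree in the first two rows. The third row is an ambiguity within 9.1.5 itself. In the last row they agree.

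**2. Whether the divergence can touch a SUSAR**

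I compared the first group in 9.1.5 with the reference safety information as quoted in 9.1.6. Abdominal pain appears in both. Vomiting, haematemesis, perforation and dysphagia appear in 9.1.5 as expected but not in the 9.1.6 text. So 4 of the 5 events, if serious and suspected to be drug-related, would count as unexpected under 9.1.6 and 9.2. Yet 9.1.5 could leave them in the CRF if the investigator deems them secondary to the cancer.

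**3. Scale, on assumptions that are not in the documents**

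Inputs: n = 20 per arm (section 10.1); r = SAE risk, assumed 10% to 40% in both arms; c = share of SAEs deemed secondary to the cancer, assumed 0% to 50%; one SAE per affected patient.

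- Reported per arm under 9.3 = n × r: 20 × 0.10 = 2, up to 20 × 0.40 = 8.
- Reported per arm under 9.1.5 = n × r × (1 − c). With c = 50%: 20 × 0.10 × 0.5 = 1, up to 20 × 0.40 × 0.5 = 4.
- Events whose route differs = n × r × c: from 0 (c = 0) to 20 × 0.40 × 0.5 = 4 per arm.
- If c were 0% on ferric maltol and 50% on control, equal true counts would appear as 2 v 1 (r = 10%) up to 8 v 4 (r = 40%).

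The last line shows what unequal attribution could do. Nothing in the documents shows that it would occur.

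**The case against.** The best defence is that little is lost. Section 9.2 keeps every adverse event on the CRF, 9.3 has the sponsor collect adverse events centrally on a database, and 9.4 captures all deaths. Serious events truly due to the cancer should also be few: surgery is with curative intent (6.1), confirmed liver or lung metastases are excluded (6.2), and the follow-up visit is at 8-12 weeks (7.7). This stands, and it limits the point to SAE notification and labelling.

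Several stronger readings are tempting, but the documents do not support them:

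- **That 9.1.5 states an exemption.** It is implied. The section nowhere says that cancer-related SAEs need not be reported, and it could be read as covering only the listed events.
- **That safety counts in general depend on the attribution.** They do not, given 9.2 and 9.4. Section 7.7 has complications and readmissions entered directly in the CRF at follow-up, and neither complications nor tolerability is said to be derived from SAE forms.
- **That 8 to 16 events are affected.** Assuming that 20% to 40% of patients have a serious event gives 0.20 × 40 = 8 to 0.40 × 40 = 16, but that is a ceiling. It would require every such event to be deemed cancer-related, and it equates patients with events.
- **That sepsis and renal failure are exempt as cancer progression.** They are listed under chemotherapy, where 9.1.5 is unclear rather than exempting.
- **That the arms will be biased.** Unequal attribution is possible in any open-label trial; here it is not shown.
- **That the termination criterion fails.** Section 10.4 uses SARs and SUSARs, which rest on causality judgement under either rule. The only added risk is that an event not submitted as an SAE misses timely sponsor review.

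**Conclusion.** The conflict is real and follows from the text alone. Sections 9.1.5, 9.3 and 9.4 cannot all be followed for a fatal event deemed secondary to the cancer, and 9.1.5 and 9.3 cannot both be followed for a non-fatal one. This assumes that 9.1.5 is read as its wording implies. SAE notifications, the timeliness of the sponsor's causality and SUSAR review, and SAE totals by arm therefore vary with the section followed and, under 9.1.5, with an unblinded attribution.

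The size cannot be derived from the documents. The illustrative 0 to 4 events per arm rests wholly on the assumed risks and attribution shares. With 20 per arm, even one or two events routed differently would visibly change an SAE table. The trial is a feasibility study with descriptive analysis (10.2), so no formal inference is at risk. The consequence is for safety oversight and for the clarity of the safety report, and it is worth correcting because correction is cheap.

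**What to change.** 1. Reconcile 9.1.5, 9.3 and 9.4 to one rule for reporting SAEs to the sponsor. This review takes no position on whether an exemption should be kept.
2. If an exemption is kept, state it identically in each of the three sections, including how it applies to deaths and to chemotherapy toxicity.
3. State in section 10 that all events meeting the 9.1.4 definition will be tabulated by arm from the CRF, with causality recorded, whatever their notification route. The CRF must therefore carry seriousness and causality for events entered as significant clinical events.

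The cost is rewording three sections, one sentence in section 10, and possibly a few more SAE forms. No visit, sample or change in sample size is needed.

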9.1.6 Suspected Unexpected Serious Adverse Reactions

A serious adverse reaction, the nature or severity of which is not consistent with the applicable product information as stated in the reference safety information in the SmPC that follows:

Common symptoms: “Abdominal pain (including upper abdomen), Flatulence, Constipation, Abdominal discomfort/ distension, Diarrhoea, Discoloured faeces, Nausea”

9.2 Recording and reporting of SAEs, SARs AND SUSARs

All AEs occurring during the study observed by the investigator or reported by the participant, whether or not attributed to study medication, will be recorded on the CRF. These adverse events will be recorded in the CRF. All SAEs assigned by the PI or delegate (or following central review) as both suspected to be related to IMP-treatment and unexpected will be classified as SUSARs and will be subject to expedited reporting to the Medicines and Healthcare Products Regulatory Agency (MHRA). The sponsor will inform the MHRA, the REC and Marketing Authorisation Holder (if not the sponsor) of SUSARs within the required expedited reporting timescales. All related AEs that result in a participant’s withdrawal from the study or are present at the end of the study, will be followed up until a satisfactory resolution occurs.

It will be left to the investigator’s clinical judgment whether or not an AE is of sufficient severity

to require the participant's removal from treatment. A participant may also voluntarily withdraw from treatment due to what he or she perceives as an intolerable AE. If either of these occurs, the participant will undergo an end of study assessment and be given appropriate care under medical supervision until symptoms cease or the condition becomes stable.

The severity of events will be assessed according to the Common Terminology Criteria for Adverse Events (CTCEA V 5.0) the following scale:

- Grade 1 Mild; asymptomatic or mild symptoms; clinical or diagnostic observations only; intervention not indicated.
- Grade 2 Moderate; minimal, local or non-invasive intervention indicated; limiting age appropriate instrumental ADL.
- Grade 3 Severe or medically significant but not immediately life-threatening; hospitalization or prolongation of hospitalization indicated; disabling; limiting self-care ADL.
- Grade 4 Life-threatening consequences; urgent intervention indicated.
- Grade 5 Death related to AE

The relationship of AEs to the study medication will be assessed by a medically qualified investigator. Any pregnancy occurring during the clinical study and the outcome of the pregnancy, will be recorded and followed up for congenital abnormality or birth defect.

9.3 Responsibilities

Principal Investigator (PI):

Checking for AEs and ARs when participants attend for treatment / follow-up.

1. Using medical judgement in assigning seriousness, causality and whether the event/reaction was anticipated using the Reference Safety Information approved for the trial.
2. Ensuring that all SAEs are recorded and reported to the sponsor within 24 hours of becoming aware of the event and provide further follow-up information

as soon as available. Ensuring that SAEs are chased with the sponsor if a record of receipt is not received within 2 working days of initial reporting.

3. Ensuring that AEs and ARs are recorded and reported to the sponsor in line with the requirements of the protocol.

Chief Investigator (CI) / delegate or independent clinical reviewer:

1. Clinical oversight of the safety of patients participating in the trial, including an ongoing review of the risk / benefit.
2. Using medical judgement in assigning the SAEs seriousness, causality and whether the event was anticipated (in line with the Reference Safety Information) where it has not been possible to obtain local medical assessment.
3. Immediate review of all SUSARs.
4. Review of specific SAEs and SARs in accordance with the trial risk assessment and protocol as detailed in the Trial Monitoring Plan.
5. Assigning Medical Dictionary for Regulatory Activities (MedDRA) or Body System coding to all SAEs and SARs.
6. Preparing the clinical sections and final sign off of the Development Safety Update Report (DSUR).

Sponsor: (NB where relevant these can be delegated to CI)

1. Central data collection and verification of AEs, ARs, SAEs, SARs and SUSARs according to the trial protocol onto a database.

2. Reporting safety information to the CI, delegate or independent clinical reviewer for the ongoing assessment of the risk / benefit according to the Trial Monitoring Plan.
3. Reporting safety information to the independent oversight committees identified for the trial (Data Monitoring Committee (DMC) and / or Trial Steering Committee (TSC)) according to the Trial Monitoring Plan.
4. Expedited reporting of SUSARs to the Competent Authority (MHRA in UK) and REC within required timelines.
5. Notifying Investigators of SUSARs that occur within the trial.
6. Checking for (annually) and notifying PIs of updates to the Reference Safety Information for the trial.
7. Preparing standard tables and other relevant information for the DSUR in collaboration with the CI and ensuring timely submission to the MHRA and REC.

Trial Steering Committee (TSC):

In accordance with the Trial Terms of Reference for the TSC, periodically reviewing safety data and liaising with the DMC regarding safety issues.

Data Monitoring Committee (DMC)

In accordance with the Trial Terms of Reference for the DMC, periodically reviewing overall safety data to determine patterns and trends of events, or to identify safety issues, which would not be apparent on an individual case basis. [name], Consultant Colorectal Surgeon, will lead the DMC.

9.4 Notification of Deaths

All deaths will be reported to the sponsor irrespective of whether the death is related to disease progression, the IMP, or an unrelated event. This report will be issued within 24 hours of the study team being notified of the death.

Reporting urgent safety measures

If any urgent safety measures are taken the CI/Sponsor shall immediately and in any event no later than 3 days from the date the measures are taken, give written notice to the MHRA and the relevant REC of the measures taken and the circumstances giving rise to those measures.

9.5 Development safety update reports

The CI will provide DSURs once a year throughout the clinical trial, or as necessary, to the Competent Authority (MHRA in the UK), where relevant the Research Ethics Committee and the sponsor. The report will be submitted within 60 days of the Developmental International Birth Date (DIBD) of the trial each year until the trial is declared ended

10 STATISTICS AND DATA ANALYSIS

10.1 Sample size calculation

No sample size calculation will be performed for this feasibility study. We will recruit a total of 40 patients to this trial (20 per arm), based on literature and guidance that 30 or more patients would be sufficient to estimate a parameter (Lancaster, Dodd et al. 2004)

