1 BACKGROUND

Colorectal cancer is associated with iron deficiency anaemia in 40-60% of cases (Leichtle, Mouawad et al. 2011). This anaemia can lead to poorer post-operative outcomes such as higher complication rates, increased length of stay and reduced survival (Muñoz, [name] et al. 2018). There has been a recent shift towards the correction of preoperative anaemia in order to optimize perioperative outcomes. However, despite improvements in preoperative haemoglobin there exists a group of patients who develop worsening or recurrent anaemia in the post-operative period. Without intervention up to 90% of patients in the immediate postoperative period may develop anaemia (Shander, Knight et al. 2004). This is not unexpected given the peri-operative blood loss; poor nutritional intake in the postoperative period; and the frequent blood sampling for laboratory tests. Our data from previous trials has demonstrated that despite preoperative intravenous iron therapy 75% of patients remain anaemic at the time of their colorectal cancer operation (Keeler, Simpson et al. 2017). In addition, our unpublished data has found that around 1/3 of patients treated with preoperative iron therapy develop a recurrence of their anaemia in the first year postoperatively. Studies have identified that traditional oral ferrous iron supplementation is largely ineffective (Bisbe et al. 2014) for the treatment of postoperative anaemia. However, a newer oral iron preparation - ferric maltol (Ferracru) has been found to be better tolerated and more efficacious than ferrous iron (Schmidt, Ahmad et al. 2016, Oppong, Lovato et al. 2018). This study aims to evaluate whether the use of iron supplementation in the form of Feracru could lead to a more sustained or improved a response in haemoglobin if given after a colorectal cancer operation. Improving this postoperative anaemia may have important implications for clinician and patient reported outcomes. The Perioperative Iron in Colorectal Cancer (PICoC) trial will run as a feasibility study to assess the proposed design, recruitability and outcome measures. Anaemic colorectal cancer patients treated with

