3.3 Outcome measures/endpoints

3.3.1 Primary endpoint/outcome

Study feasibility will be the primary endpoint. No a priori criteria will be used to determine study feasibility. We will use the data generated by PICoC to determine the sample size and outcome measures of a definitive trial

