7.3 The Randomisation scheme

Randomisation will be undertaken via an online platform in a 1:1 fashion to either the control group (standard care) or the intervention group (postoperative ferric maltol). The study will be an open label design and participants will be informed of their group allocation after their operation. Randomisation alerts with allocation details will be emailed to the CI, research fellow, research nurses and the pharmacy team.

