7.8 Withdrawal criteria

There will be intention-to-treat analyses carried out. Analysis of all participants who have been randomised will be undertaken regardless of withdrawal. The reason for withdrawal will

be recorded in the CRF. Each participant has the right to withdraw study at any time. A participant will be withdrawn from the study if any of the following occurs:

- Absence of anaemia on postoperative days 2, 3 and 5.
- Pregnancy
- Ineligibility (either arising during the study or retrospective having been inadvertently overlooked at screening)
- Significant protocol deviation as defined by the CI
- An adverse event which requires discontinuation of the study medication or results in inability to continue to comply with study procedures
- Disease progression which requires discontinuation of the study medication or results in inability to continue to comply with study procedures
- Patients who do not undergo an operation as a result of a change in fitness for surgery will be excluded.
- Consent withdrawn.
- Lost to follow up

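### The 30-patient benchmark in Section 10.1 is missed for parameters that exist only in the ferric maltol arm (at most 20 patients) and is not assured for pooled 8-12 week outcomes

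*Combined protocol and SAP*

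**What the plan says.** Section 10.1 is explicit that "No sample size calculation will be performed for this feasibility study". It sets recruitment at 40, split 20 and 20, and rests this on cited guidance that "30 or more patients would be sufficient to estimate a parameter". It does not say which parameter is meant, whether 30 is a total or a per-arm count, or whether it counts recruited or evaluable patients. It gives no attrition allowance and no replacement rule.

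Section 3.3.1 states the purpose: "We will use the data generated by PICoC to determine the sample size and outcome measures of a definitive trial". Section 10.2 repeats it and plans a descriptive analysis. Section 10.3.2 lists compliance with randomised treatment among the primary feasibility outcomes. Section 8.8 describes compliance only for ferric maltol, declared by the patient at the final visit. Tolerability of ferric maltol is a secondary objective (Section 3.2).

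Several rules reduce the number followed to 8-12 weeks. Section 7.8 withdraws patients for "Absence of anaemia on postoperative days 2, 3 and 5" and excludes those whose operation does not go ahead. Section 10.5 excludes patients with unrecoverable missing data. Section 7.8 also says that everyone randomised is analysed, withdrawn or not.

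On likely anaemia rates, Section 1 reports from earlier trials that "despite preoperative intravenous iron therapy 75% of patients remain anaemic at the time of their colorectal cancer operation", and separately that up to 90% may be anaemic soon after surgery if nothing is done.

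**The concern.** The only support for the sample size is a single threshold applied to the recruited total. Some of the quantities the trial is meant to deliver are not estimated on that total. Controls receive standard care, so they contribute nothing to compliance with, or tolerability of, the study drug. Change in haemoglobin and quality of life at 8-12 weeks can be observed only in patients still being followed, and the design removes some by rule.

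What is at stake is the definitive trial. If its assumed compliance and SD are taken from PICoC as point estimates, with 10.1 implying that they are adequately estimated, that trial may be materially under- or oversized with nothing in the plan to warn of it.

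**Working it through.** **The plan's own figure.** 2 × 20 = 40, and 40 ≥ 30. There is no power, effect size, SD or dropout input, so no formula can reproduce 40. The check is whether the benchmark is met for each type of parameter.

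**1. Intervention-only parameters.** Denominator at most 20, and 20 < 30. This needs no assumption.

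**2. Pooled 8-12 week outcomes.** Expected evaluable = 40 × P(anaemic) × (1 − other loss). P(anaemic) is 0.75 or 0.90, from Section 1. Neither is the rate the design needs, which is anaemia on day 2, 3 or 5 after intravenous iron: 75% is measured before surgery and 90% is an upper limit without intervention. Other loss has no figure in the documents; 0%, 10% and 20% are my assumptions. P(at least 30) is the exact binomial tail for 40 independent patients.

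| P(anaemic) | Other loss (assumed) | Expected evaluable | Per arm | P(at least 30) |
|---|---|---|---|---|
| 0.75 | 0% | 40 × 0.75 = 30.0 | 15.0 | 0.58 |
| 0.75 | 10% | 30 × 0.90 = 27.0 | 13.5 | 0.20 |
| 0.75 | 20% | 30 × 0.80 = 24.0 | 12.0 | 0.04 |
| 0.90 | 0% | 40 × 0.90 = 36.0 | 18.0 | 0.999 |
| 0.90 | 10% | 36 × 0.90 = 32.4 | 16.2 | 0.88 |
| 0.90 | 20% | 36 × 0.80 = 28.8 | 14.4 | 0.41 |

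At 90% anaemic, other loss can reach 1 − 30/36 = 16.7% before the expected total falls below 30. At 75% there is no margin.

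**3. Precision of a proportion.** Wilson 95% CI for an observed 80%:

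- n = 40 (32/40): 65.2-89.5%
- n = 30 (24/30): 62.7-90.5%
- n = 20 (16/20): 58.4-91.9%
- n = 15 (12/15): 54.8-93.0%

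**4. Effect on the definitive sample size.** The 95% limits for a pooled two-arm SD, as multiples of the estimate, are √(df/χ²) at the 97.5% and 2.5% points, with df = evaluable total − 2. For a comparison of means at a fixed difference, sample size is proportional to SD², so these limits are squared.

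- 40 evaluable, df 38: 0.817-1.289; squared, 0.67-1.66
- 30 evaluable, df 28: 0.794-1.352; squared, 0.63-1.83

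This assumes approximate normality and a common SD in the two arms.

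**5. What is not affected.** Eligibility uses everyone screened and consent everyone approached. Withdrawal and retention keep the recruited or randomised denominator, and withdrawal for absence of anaemia is itself a feasibility result.

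**The case against.** The strongest reply is that a feasibility study needs no power calculation, that 10.1 claims none, and that 40 exceeds 30. The benchmark is not stated per arm, so requiring 30 in each arm would be an outside reading. Most primary measures keep full denominators, Section 7.8 keeps all randomised patients in the analysis, and the SD intervals apply to any study of this size. Nearly all of this stands. It does not help the intervention-only parameters: the rule is worded for estimating a parameter, and drug compliance is a parameter with at most 20 patients behind it. Nor does analysing everyone randomised create 8-12 week measurements for patients already withdrawn.

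A reader might go further and infer that the plan's own anaemia figures leave only 24-36 evaluable, so that the stated adequacy is not delivered at all. The documents do not support that. Those figures give 30-36; reaching 24 takes a further 20% loss on top of the 75% figure, which is an assumption. The 75% may also overstate withdrawal. It precedes surgical blood loss, patients have up to three tests at which to qualify, and the postoperative threshold (130/120 g/L) is easier to fall below than the entry threshold (120/110 g/L).

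A reader might also note that Section 4 places randomisation before surgery and Section 7.7 after it. In either case it precedes the day 2 test, so the point about withdrawal does not depend on which is followed.

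**Conclusion.** The point holds in two parts of different strength. For compliance with and tolerability of ferric maltol, the plan's benchmark is missed outright: at most 20 against 30, with no assumption needed. For pooled 8-12 week outcomes it is met at recruitment and not assured afterwards. The chance of 30 or more evaluable runs from 0.58 to 0.999 across the two background anaemia figures with no other loss, and from 0.04 to 0.41 with an assumed 20% loss. These figures are illustrative, since the documents give neither the relevant anaemia rate nor any attrition rate.

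This is not an arithmetic error in 10.1, and it does not show that 40 is too few for a feasibility study. The justification is broader than the design supports, and the plan states no precision for estimates meant to size the next trial. The change should be made.

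**What to change.** Keep 40 patients. In Section 10.1:

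- claim the 30-patient benchmark only for parameters estimated on the pooled sample, and say that drug compliance and tolerability rest on at most 20;
- give the expected evaluable number at 8-12 weeks after postoperative withdrawal, exclusions and loss, naming the rates assumed;
- give the expected precision, for example the 95% CI for an observed 80%: 65-90% at n = 40, 63-90% at n = 30, 58-92% at n = 20, 55-93% at n = 15.

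In Section 10.2, report the definitive-trial sample size as a range over the 95% CI of the pooled SD, not as a single number. On current numbers that range is 0.67-1.66 times the point value on 38 degrees of freedom, or 0.63-1.83 times on 28.

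The cost is a paragraph in 10.1 and a sentence in 10.2, with no more patients and no change in conduct. The downside is that the stated adequacy becomes less favourable.
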